1 INTRODUCTION

This statistical analysis plan (SAP) provides details and specifications for the statistical analyses of data collected under Marinus Pharmaceuticals, Inc. Protocol 1042-SC-2001, “A Phase 2 Open-label 12-Week Trial of Adjunctive Ganaxolone Treatment (Part A) in Tuberous Sclerosis Complex-related Epilepsy followed by Long-term Treatment (Part B)” (Version 2, Protocol Amendment 1, 12 May 2020).

The structure and content of this SAP provide sufficient detail to meet the requirements identified by the US Food and Drug Administration (FDA) and International Conference on Harmonization (ICH) of Technical Requirements for Registration of Pharmaceuticals for Human Use: Guidance on Statistical Principles in Clinical Trials.¹ All work planned and reported for this SAP will follow internationally accepted guidelines for statistical practice published by the American Statistical Association².

The following documents were also considered in preparation in writing this SAP:

- ICH E3 Guideline: Structure and Content of Clinical Study Reports³
- ICH E6 Guideline: Good Clinical Practice⁴
- ICH E8: General Considerations for Clinical Trial⁵
- ICH E9: Statistical Principles for Clinical Trials⁶

The SAP is a supplement to the study protocol which should be references for additional details on study design, study conduct, and other operational aspects of the study.

1.1 STUDY OBJECTIVES

1.1.1 Primary Objective

The primary objective of this study is to assess preliminary safety and efficacy of Ganaxolone (GNX) adjunctive therapy for the treatment of primary seizure types in patients with genetically- or clinically-confirmed Tuberous Sclerosis Complex (TSC) - related epilepsy through the end of the 12-week treatment period. The primary seizure types (focal motor seizures without impairment of consciousness or awareness, focal seizures with impairment of consciousness or awareness, focal seizures evolving to bilateral, tonic-clonic convulsive seizures, and generalized motor seizures including tonic-clonic, bilateral tonic, bilateral clonic, or atonic/drop seizures) are identified to be the most common, easily identifiable/countable by a parent/caregiver/legally authorized representative (LAR), and are most consequential to the patient’s quality of life.

1.1.2 Secondary Objectives

The secondary objectives of this study are the following:

- To assess the long-term efficacy of GNX when administered as adjunctive therapy throughout the open-label extension (OLE) period (Part B).
- To assess the long-term safety and tolerability of GNX when administered as adjunctive therapy throughout the OLE period (Part B).

- [REDACTED]
- [REDACTED]
- [REDACTED]
- [REDACTED]
- [REDACTED]

1.2 STUDY ENDPOINTS

Primary, secondary and exploratory efficacy endpoints described below support the primary study objective of assessing the efficacy of investigational product (IP), GNX, as adjunctive therapy for the treatment of primary seizure types in patients with TSC-related epilepsy through the end of the 12-week treatment period (Part A) and exploratory objectives related to Part A of the study.

Endpoints supporting the secondary study objective of assessing long-term efficacy of GNX with administered as adjunctive therapy throughout the OLE period (Part B) are described in [Section 1.2.5](#) (Open-Label Extension Endpoints).

1.2.1 Primary Efficacy Endpoint

The primary efficacy endpoint (change in seizure frequency) is the percent change in 28-day seizure frequency through the end of the 12-week treatment period (4-week titration and 8-week maintenance) relative to the baseline, based on the primary seizure types. The primary seizure types are defined as the following: focal motor seizures without impairment of consciousness or awareness, focal seizures (motor or non-motor) with impairment of consciousness or awareness, focal seizures evolving to bilateral, tonic-clonic convulsive seizures, and generalized motor seizures including tonic-clonic, bilateral tonic, bilateral clonic, or atonic/drop seizures. Focal aware non-motor and generalized seizures without motor features, infantile or epileptic spasms, and myoclonic seizures do not count as the primary seizure types.

The calculation of post-baseline 28-day seizure frequency and percent change in 28-day seizure frequency are explained in [Section 3.1.3](#).

1.2.2 Secondary Efficacy Endpoints

In addition to evidence about effects of GNX on 28-day seizure frequency, the clinical trial will assess GNX's effects on several secondary endpoints that capture important symptoms and activities of daily living that are meaningfully compromised by TSC.

1.2.2.1 Secondary Efficacy Endpoint – Seizure Control

- Percentage of patients experiencing a $\geq 50\%$ reduction in 28-day primary seizure frequency through the end of the 12-week treatment period compared to the 4-week baseline period.

Derived seizure secondary efficacy endpoints will be based on data through the end of the 12-week treatment period relative to the 4-week baseline period as defined in [Section 3.1.3](#).

1.2.2.2 Secondary Efficacy Endpoint – Other

- CGI-I – parent/caregiver and clinician
- CGI-C - target behavior

These behavioral/neuropsychiatric secondary endpoints will provide information about the overall impact of GNX on the treatment of patients with TSC. The CGI-C and the CGI-I are 7-point scales used to assess change after initiation of GNX. The scores range from 1 = very much improved to 7 = very much worse. Separate CGI-I responses will be collected the patient's parent/caregiver and the clinician at baseline, Week 5 and Week 12 of Part A of the study and at the final visit in Part B, if applicable. The CGI-C will be completed by the patient's parent/caregiver at the same study visits.

■ [REDACTED]

■ [REDACTED]

■ [REDACTED]

■ [REDACTED]

1.2.4 Safety Endpoints

Safety and tolerability endpoints for Part A and Part B include:

- Vital signs (height, weight, blood pressure [BP], heart rate [HR], respiratory rate [RR], body temperature)
- Electrocardiograms (ECGs)
- Clinical laboratory tests (hematology, chemistry and urinalysis)
- Physical exam findings
- Neurological exam findings
- Developmental exam findings
- Columbia-Suicide Severity Rating Scale (C-SSRS), if appropriate
- Adverse events (frequency, type and severity)

1.2.5 Open-Label Extension Endpoints

To evaluate the secondary study objectives of assessing the long-term efficacy and safety of GNX, the following endpoints defined above for Part A of the study will be examined in patients participating in Part B of the study:

- Primary seizure frequency during OLE: change in 28-day primary seizure frequency from baseline (Visit 1 to Visit 2) to the OLE period (Visit 5 through Visit 8)
- Percent change in primary seizure frequency during OLE relative to the baseline period.
- Primary seizure frequency across 12-week treatment period and OLE: change in 28-day primary seizure frequency from baseline (Visit 1 to Visit 2) to the cumulative treatment periods A and B (Visit 2 through 8)

- Percent change in primary seizure frequency baseline versus cumulative treatment periods (12-week treatment period + OLE)
- Seizure frequency for all types of seizures in OLE versus baseline and cumulative treatment Parts A and B versus baseline
- Percent change in all-types seizure frequency in OLE versus baseline and cumulative treatment Parts A and B versus baseline
- CGI-C for target behaviour: Week 36 and final visit of the OLE
- CGI-I, parent/caregiver and clinician: Week 36 and final visit of the OLE.
- [REDACTED] at the final OLE visit.
- Safety endpoints listed in [Section 1.2.4](#).

1.3 STUDY DESIGN

1.3.1 General Study Design and Plan

This is an open-label (OL) proof of concept study of adjunctive GNX treatment in patients with a confirmed clinical diagnosis of TSC and/or a mutation in either the *TSC1* or *TSC2* gene. The trial consists of two parts ([Figure 1](#)): Part A consists of a 4-week baseline period followed by a 12-week treatment period (4-week titration and 8-week maintenance). For patients not continuing in the 24-week OLE period (Part B), a 2-week taper period followed by a 2-week safety period would follow. The main difference between Part A and Part B is the length of treatment, less frequent assessments, and the ability to alter drug doses (both GNX and other antiepileptic drug [AED] treatments which includes initiating and stopping other medications) based on investigator evaluation of the patient's clinical course during Part B. Patients with a seizure frequency reduction rate of $\geq 35\%$ during the 12-week treatment period in Part A compared to baseline may continue into Part B ("OLE eligible"). If the investigator believes there is a medical benefit for the patient who does not meet the seizure reduction criterion to enter the OLE, they must discuss the patient with the sponsor medical monitor and receive sponsor approval for that patient to continue into the OLE.

The Schedule of Assessments from the protocol for both Part A and Part B are included in Appendix A and Appendix B, respectively, of this document.

Part A

- 4-week baseline period
- 4-week titration period
- 8-week maintenance period
- 2-week taper period (For patients who do not complete Part A or after completing

[figure not shown]
Part A but do not continue into Part B)

- 2-week safety follow-up visit post taper (For patients who taper off GNX)

Part B (Optional for OLE-eligible patients)

- 24-week OLE period
- 2-week taper period (For patients who discontinue GNX due to early termination or completion)
- 2-week safety follow-up visit post-taper (For patients who taper off GNX)

Figure 1: Study Design

1.3.2 Sample Size Estimation

Approximately 36 TSC patients, aged 2 to 65 inclusive, will be screened to achieve 30 TSC patients given IP in Part A. Since this is an OL proof of concept study, sample size was not determined by statistical methods.

1.3.3 Randomization and Blinding

This is an open-label study. Randomization and blinding are not applicable for this study.

2 STATISTICAL CONSIDERATIONS

2.1 GENERAL CONSIDERATIONS

Statistical analyses will be performed using SAS System, Version 9.4 or higher (SAS Institute, Inc., Cary, NC).

No formal hypothesis testing will be performed for this study. Data will be summarized descriptively. Separate summaries will be presented for data collected in Part A and data collected in Part B of the study. Unless otherwise specified, descriptive statistics for continuous variables will include number of non-missing observations (n), arithmetic mean, standard deviation (SD), 25th and 75th percentiles, minimum, median and maximum. For categorical variables, descriptive statistics including counts and percentages will be used. Only observed data will be summarized. Missing data will not

be imputed. Scheduled assessments will be included in summaries with the exception of reports of abnormal laboratory, vital sign, or ECG values.

Study data from all assessments (scheduled and unscheduled) will be displayed in individual data listings by study part (Part A or Part B), patient and visit, if applicable.

2.2 ANALYSIS SETS

Analysis sets for this study are defined as:

- Screened population: all patients who have signed informed consent for the study.
- Safety population: all patients who have received at least one dose of GNX
- Intent-to-treat (ITT) population: all patients who receive at least one dose of GNX and have at least one post-baseline efficacy assessment.
- Per-protocol (PP) population: includes all ITT patients without major protocol violations, as will be defined prior to database lock. Patients that fall below 80% compliance at two consecutive visits during the maintenance period (i.e. Visits 4 and 5, Weeks 5 and 12) will not be included in the PP population.
- Open-label extension (OLE) population: includes all ITT patients who participate in the OLE (Part B) of the study and receive at least one dose of GNX in the Part B.
- Pharmacokinetic (PK) population: all ITT patients who have had at least one PK sample collected and a valid bioanalytical result obtained. Pharmacokinetic data collected from this population may be reported separately.

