9.5. Analysis Populations

The intent-to-treat (ITT) population comprises all patients who receive at least one dose of IP. The ITT population will be the primary population for efficacy analyses. The PP population includes all ITT patients without major protocol violations (defined prior to database lock). Safety will be reported for all patients.

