4.2 EFFICACY ANALYSES

4.2.1 Primary Efficacy Analysis

4.2.1.1 Primary Analysis

The primary efficacy endpoints, the percent change in 28-day primary seizure type frequency through the end of the 12-week treatment period (Part A; 4-week titration and 8-week maintenance) relative to the baseline, is defined in Section 1.2.1. The calculation of the primary endpoint is described in Section 3.1.3.

Descriptive summaries including the number of patients with non-missing primary seizure data, mean arithmetic change and percent change in 28-day primary seizure type frequency from baseline and associated 95% confidence intervals, SD, minimum, median and maximum values will be presented for the baseline period, 4-week titration period, 8-week maintenance period and 12-week treatment period. All patients in the ITT population and all available seizure data within Part A of the study will be included in these analyses regardless of whether the patient stopped taking IP or took rescue medication.

Additionally, a by-patient listing of seizure data collected during Part A will be provided.

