4.2.2 Secondary Efficacy Analysis

Secondary efficacy endpoints are defined in Section 1.2.2. Analyses of secondary

efficacy endpoints will be based on the ITT population.

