4.2.2.1 Seizure Control

To assess seizure control during the 12-week treatment period, the subset of ITT patients who achieve $\geq 50\%$ reduction in 28-day primary type seizure frequency during the 12-week treatment period compared to baseline will be summarized as was described for the primary efficacy analysis. The calculation of percent reduction from baseline in seizure frequency is described in Section 3.1.3.6.

Percent change values meeting criteria of interest, i.e. $\geq 25\%$ reduction, $\geq 50\%$ reduction and $\geq 75\%$ reduction from baseline will be flagged in the by-patient listing of seizure data.

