6 SUMMARY OF MAJOR CHANGES IN THE PLANNED ANALYSES

No changes to planned analyses are anticipated. Any further analysis changes made after this SAP is finalized will be documented with an SAP amendment or described in the clinical study report (CSR).

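### The SAP's ITT set is narrower than the protocol's, and no rule classifies dosed patients without post-baseline data, so the ≥50% responder percentage can only be pushed up

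*SAP*

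**What the plan says.** Protocol 9.5: "The intent-to-treat (ITT) population comprises all patients who receive at least one dose of IP". It continues: "The ITT population will be the primary population for efficacy analyses". The protocol synopsis says the same.

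SAP 2.2 gives the ITT population as "all patients who receive at least one dose of GNX and have at least one post-baseline efficacy assessment". The protocol's all-dosed set does appear in SAP 2.2, but as the Safety population: "all patients who have received at least one dose of GNX".

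The narrower set is the one used for efficacy. For the primary analysis, SAP 4.2.1.1 states: "All patients in the ITT population and all available seizure data within Part A of the study will be included in these analyses". SAP 4.2.2 says of the secondary endpoints that analyses of "efficacy endpoints will be based on the ITT population". For the responder endpoint, SAP 4.2.2.1 speaks of "the subset of ITT patients who achieve" a reduction of at least 50%. It does not say how a patient without post-baseline seizure data is classified.

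On missing data, SAP 2.1, 3.3 and 3.3.2 summarise observed data only and impute nothing for seizures. SAP 6 states: "No changes to planned analyses are anticipated".

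**The concern.** One name carries two definitions for the set on which efficacy is reported. The SAP's extra condition is a post-treatment event: membership depends on what happens after the first dose. A dosed patient with no post-baseline efficacy data cannot appear as a responder, so leaving that patient out shortens the denominator and never the numerator.

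The trial has one arm and about 30 patients. No comparator offsets a one-sided shift, and each patient carries about 3 percentage points (1/30 = 3.3%). At stake is the accuracy of a descriptive responder percentage. With no hypothesis test planned, neither type I error nor power is involved.

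**Working it through.** **No plan figure to reproduce.** Protocol 9.4 and SAP 1.3.2 state that the sample size has no statistical derivation. Neither document gives a responder rate or a dropout rate. The check compares the definitions and then does simple arithmetic on assumed counts.

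**Step 1: who differs.** Protocol ITT = all dosed. SAP ITT = all dosed minus those with no post-baseline efficacy assessment. Call the number removed k.

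**Step 2: percent change.** SAP 3.1.3.2 and 3.1.3.3 need a post-baseline frequency, which is seizures divided by days with diary data, times 28. With no such days the quantity does not exist, and SAP 3.3.2 imputes nothing. A patient with no post-baseline seizure data therefore adds no value under either definition, and the mean and median stay the same.

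**Step 3: responder percentage.** Let r be the number of responders among 30 dosed (the planned number, SAP 1.3.2).

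- All dosed as denominator, patients without data counted as non-responders: r/30.
- SAP set: r/(30 − k).
- Difference: r/(30 − k) − r/30 = rk / [30(30 − k)], which is zero when k = 0 and positive for any k > 0 and r > 0.

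Both r and k are assumed. With r = 10, the all-dosed rate is 10/30 = 33.3% (exact 95% CI 17.3 to 52.8).

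| k | SAP set | Rate | Difference (points) |
|---|---|---|---|
| 0 | 10/30 | 33.3% | 0 |
| 1 | 10/29 | 34.5% | 10/870 = 1.1 |
| 2 | 10/28 | 35.7% | 20/840 = 2.4 |
| 3 | 10/27 | 37.0% (exact 95% CI 19.4 to 57.6) | 30/810 = 3.7 |

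Other values of r, again for k = 1, 2, 3:

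- r = 6: 20.7%, 21.4%, 22.2% against 20.0%.
- r = 15: 51.7%, 53.6%, 55.6% against 50.0%.

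Over this range the shift runs from 0.7 to 5.6 points.

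**Step 4: does aligning the definition remove the shift?** Not by itself. Protocol 9.5 and 9.6.2.1 do not say that a dosed patient without data is a non-responder, and Protocol 9.3 leaves missing data to the SAP. With ITT set to all dosed but the SAP's observed-data rule (2.1, 3.3) left as it is, the analyst could still report 10/27. The shift goes only when the definition and a non-responder rule are stated together.

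**Step 5: what counts as an efficacy assessment.** The SAP does not define the term. Protocol 7.5 names the daily seizure diary, so one diary day after the first dosing day would suffice on the natural reading. If the term meant the CGI scales, first collected after baseline at Week 5 (Protocol 7.5.2 and 7.5.3), more patients would be lost. Some of them would have diary data, and then the results of Steps 2 and 3 would no longer be assured for them.

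**The case against.** The strongest reply is that very few patients can fall into the gap. The diary is daily, and entries are due within 48 hours (Protocol 9.1). Telephone reviews of the diary are planned on Days 1, 2 and 3 (Protocol 7.2.3). Patients who stop the drug are encouraged to keep the diary to the end of maintenance (Protocol 3.1), and SAP 4.2.1.1 keeps their data whether or not they stopped. On the diary reading, exclusion needs essentially no entry after the first dosing day. This stands, and k may well be zero. It limits the size of the point but does not reconcile the two definitions.

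It can also be said that the SAP would make any exclusion visible. SAP 4.1.1 reports the numbers dosed and the numbers in each analysis set, and 4.2.1.1 reports the number with non-missing primary seizure data. That is true and useful, but a visible exclusion still leaves a higher headline percentage.

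A reader might infer several stronger things that the documents do not support:

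- **That the primary result is biased.** A patient without post-baseline seizure data has no percent change under either definition.
- **That the protocol itself yields 10/30.** That figure also needs a non-responder rule, which neither document states.
- **That everyone who stops early is lost, mainly for intolerance.** Stopping the drug does not remove a patient from the SAP's ITT, and no document gives the number or the reasons.
- **That the PP, OLE and PK sets are materially distorted because each is built on ITT.** OLE entry requires a calculated seizure reduction over Part A or a sponsor-approved exception, and the first PK sample is at Week 5. Such patients will almost always have diary data, so the effect is negligible.
- **That SAP 6 conceals a change.** SAP 1 says it is written to the protocol amendment of 12 May 2020, which is not among the documents reviewed. The protocol in hand is dated 11 Jun 2021. Whether the SAP departed from the protocol it cites cannot be checked.

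**Conclusion.** The contradiction between Protocol 9.5 and SAP 2.2 is real and should be resolved. Its numerical consequence is confined to the ≥50% responder percentage and can only be upward. With 30 dosed and 10 responders assumed, the shift is about 1 to 4 points for one to three patients without post-baseline data, and zero if there are none. That is small beside an exact interval of about 17% to 53%.

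The conclusion is certain for the difference in wording and for the direction of the shift. It is open for the size, because k is not known. The direction and the unchanged percent change both rest on reading an efficacy assessment as at least one post-baseline diary day.

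**What to change.** Make two changes to the SAP, together:

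1. In SAP 2.2, define ITT as all patients who took at least one dose, as in Protocol 9.5. The undefined assessment term then no longer decides membership, and the SAP's PK set comes into line with Protocol 9.9.
2. In SAP 4.2.2.1, state that the ≥50% responder percentage uses all dosed patients as its denominator, and that patients lacking post-baseline diary data count as non-responders.

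Nothing need be added for the percent change, since SAP 4.2.1.1 already reports the number of patients with data. The cost is SAP wording and a responder rate that may come out slightly lower. No new data, visits or patients are required.

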6.5. Patient Compliance

Patient compliance will be tracked through the seizure and medication diary. Parent/caregiver are to record daily seizure frequency and type in addition to study medication and non-study AED administration. Compliance with IP treatment will be assessed by inspecting the seizure and medication diary entries and returned supplies with queries as necessary. Parent/caregiver will be re-educated on the importance of adhering to daily seizure, IP and non-study AED recording as needed. Patients that fall below 80% compliance at 2 consecutive visits during the maintenance period will not be in the Per-Protocol (PP) population.

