7.2.5. Titration Period (Phone Follow-ups, Weeks 2, 3, and 4 ± 3 days)

A telephone follow-up visit will be conducted at Weeks 2, 3, and 4 (\pm 3 days) to assess the following:

- AEs
- Seizure and medication diary review

7.2.6. Maintenance Period (Visits 4 and 5, Weeks 5 and 12 ± 3 days)

The following study procedures/assessments will be completed at Weeks 5 and 12 (\pm 3 days):

- Vital signs (to include BP, HR, RR, and body temperature)
- Weight
- Physical, neurological, and developmental examination (developmental examination is limited to pediatric patients 2 to 17 years of age, inclusive)
- ECG
- Clinical laboratory tests (chemistry and hematology)
- Urinalysis
- Drug screen (plasma) for THC and CBD (Visit 5 [Week 12])
- Serum pregnancy test for all girls/women of childbearing potential
- IP PK sample (Visit 4 [Week 5], between 1-5 hours after last IP dose and Visit 5 [Week 12], between 4-8 hours after last IP dose)
- Concomitant AED review and levels if per standard of care
- [REDACTED]
- AEs
- Seizure and medication diary review
- [REDACTED]
- CGI-C (parent/caregiver/LAR identified behavioral target)
- CGI-I (parent/caregiver/LAR and clinician)
- C-SSRS (since previous visit). Only for patients \geq 7 years old if appropriate, otherwise clinical judgement will be used.

- Dispense IP

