3.1.3.2 Post-baseline seizure frequency – Maintenance Period, Part A, Part B and Overall

Post-baseline 28-day seizure frequency will be calculated as the total number of seizures in the specified post-baseline period divided by the number of days with non-missing seizure data in the same post-baseline period, multiplied by 28. Within Part A of the study, post-baseline seizure activity will be determined based on the days following the first day after the date of the first dose of IP. The first day of treatment is included in neither the baseline nor the post-baseline period since seizures reported on that date could have occurred either before or after the initiation of treatment. Within Part B (OLE

period), post-baseline seizure activity will be determined by the first day of OLE treatment.

Separate frequencies will be calculated for the 8-week maintenance period of Part A (Maintenance), Parts A (12-week treatment period consisting of a 4-week titration period and an 8-week maintenance period) and B of the study (OLE period of up to 24 weeks) and across both study parts.

Post-baseline specified study period 28-day seizure frequency =

$$\frac{\# \text{ seizures, specified study period}}{\# \text{ specified study period days with seizure data reported}} \times 28$$

3.1.3.3 Percent change in 28-day seizure frequency – Maintenance Period, Part A, Part B and Overall

% change from baseline =

$$\frac{[(\text{post-baseline 28-day seizure frequency}) - (\text{baseline 28-day seizure frequency})]}{(\text{baseline 28-day seizure frequency})} \times 100$$

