3.2 ANALYSIS VISIT WINDOWS

Efficacy Analyses

Efficacy analyses will use data only from scheduled visits. Data will be reported by designated visit.

Data collected at unscheduled visits will be provided in listings.

For analysis of data collected across specific study periods, the following definitions will be applied:

- Baseline period: Visit 1 to Visit 2; Study Week -4 (Day -32 ± 4) through Study Day 0 (date of first dose of IP)
- Titration period: Visit 2 + 1 day to Visit 4; Study Day 1 through Study Week 4 (Day 28 ± 3 days; date of Visit 4)
- Maintenance period: Visits 4 + 1 day and 5; Study Week 5 (± 3 days) through Study Week 12 (± 3 days)
- 12-week treatment period: titration period + maintenance period (including taper and safety visits if not continuing in OLE)
- OLE period if continuing in OLE: Visit 5 + 1 day through final visit

Safety Analyses

Safety data will be summarized by actual visit. No visit windowing will be applied.

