4.2.1.2 Sensitivity Analysis

The primary analysis will be repeated in the PP population.

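### The SAP's Per-Protocol compliance rule requires failure at both Visit 4 and Visit 5, so a patient who stops drug at Week 5 can stay in the Per-Protocol set

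*SAP*

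**What the plan says.** SAP 2.2 gives two routes out of the PP set. The general one is that the set "includes all ITT patients without major protocol violations, as will be defined prior to database lock". The specific one is the compliance rule: "Patients that fall below 80% compliance at two consecutive visits during the maintenance period (i.e. Visits 4 and 5, Weeks 5 and 12".

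Protocol 6.5 has the same threshold but does not say which visits count: "Patients that fall below 80% compliance at 2 consecutive visits during the maintenance period will not be in the Per-Protocol (PP) population". Protocol 7.5.1 repeats this. The clinic visits are fixed by the heading of protocol 7.2.6, "Maintenance Period (Visits 4 and 5, Weeks 5 and 12 ± 3 days". Protocol 7.2.7 adds a telephone visit at Week 9, also in maintenance, at which the seizure and medication diary is reviewed.

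Part A treatment is described in SAP 3.1.3.2 as "consisting of a 4-week titration period and an 8-week maintenance period". For analysis, SAP 3.2 uses visit dates instead: "Titration period: Visit 2 + 1 day to Visit 4" and "Maintenance period: Visits 4 + 1 day and 5".

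SAP 3.1.3.7 computes compliance from the eDiary as days with drug taken divided by days with drug status reported. It gives no look-back interval for compliance at a visit. The PP set has one efficacy use, in SAP 4.2.1.2: "The primary analysis will be repeated in the PP population".

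**The concern.** With Visits 4 and 5 named, the rule is a joint condition on two values, and passing either one protects the patient. The Visit 4 value says little about maintenance, because most or all of its days are titration days. Visit 5 is the only one of the two that covers the bulk of maintenance, and failing it alone does not exclude.

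The situation is foreseeable. The protocol expects some patients to stop drug during maintenance and asks them to keep their diaries until it ends. SAP 4.2.1.1 includes all Part A seizure data whether or not the patient stopped drug, and the PP analysis repeats that calculation. Off-drug diary days from an early stopper would therefore enter the PP estimate as well as the ITT estimate. The PP repeat is the only planned sensitivity analysis of the primary endpoint and the only planned efficacy summary restricted by adherence.

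**Working it through.** The plan gives no figure of its own to reproduce, so the check applies the stated rule to example patients.

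**Inputs**
- Nominal periods: titration Days 1-28, maintenance Days 29-84, which is 56 days (SAP 3.1.3.2).
- Nominal visit days: Visit 3 = Day 7, Visit 4 = Day 35, Visit 5 = Day 84, each ± 3 days (schedules of assessments). SAP 3.2 also attaches Day 28 to the date of Visit 4; I use Week 5, as in SAP 2.2 and the schedules.
- Maintenance under SAP 3.2: Days 36-84, which is 49 days.
- Compliance = 100 × days taken / days reported (SAP 3.1.3.7).
- Assumptions: every day is reported, and drug is taken daily until an abrupt stop.

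**1. What Visit 4 measures.** Titration is 28/35 = 80% of the interval since Visit 2, or 21/28 = 75% of the interval since Visit 3. Under SAP 3.2 it is the whole interval.

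**2. Drug taken to Day 35, none after.**
- Visit 4: 35/35 since Visit 2, 28/28 since Visit 3, or 7/7 if only Days 29-35 count. All are 100%.
- Visit 5: 0/49 = 0% since Visit 4, or 35/84 = 41.7% cumulatively.
- This is one pass and one failure, so the rule does not remove the patient under any of these look-backs.
- Maintenance days dosed: 7/56 = 12.5% nominal, or 0/49 under SAP 3.2.

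**3. Earlier stops.** Here the look-back matters.

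| Last dosed day | Visit 4 since Visit 2 | Visit 4 since Visit 3 | Nominal maintenance dosed |
|---|---|---|---|
| 30 | 30/35 = 85.7%, kept | 23/28 = 82.1%, kept | 2/56 = 3.6% |
| 28 | 28/35 = 80.0%, kept (not below 80%) | 21/28 = 75.0%, removed | 0/56 = 0% |

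If Visit 4 counted only Days 29-35, the Day 30 stopper would score 2/7 = 28.6% and be removed. With Visit 4 between Day 32 and Day 38, the lowest nominal maintenance dosing still kept under the two tabulated look-backs runs from 0% to 7.1%.

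**4. If the Week 9 telephone visit counts (protocol wording).** For the Day 35 stopper, Days 36-63 give 0/28 and Days 64-84 give 0/21. Cumulatively the values are 35/63 = 55.6% and 35/84 = 41.7%. Both consecutive visits fail and the patient is removed.

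**5. Taper.** If the stop after Day 35 is followed by a 14-day taper recorded as drug taken, Visit 5 since Visit 4 is 14/49 = 28.6% and nominal maintenance dosing is (7 + 14)/56 = 37.5%. The patient still fails only at Visit 5 and is kept.

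**6. Denominator.** Suppose the patient stops both drug and diary after Day 35. Counting reported days only, compliance from Day 29 is 7/7 = 100%; over the SAP 3.2 period it is 0/0, which is undefined. With all days of the SAP 3.2 period in the denominator it is 0/49.

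**The case against.** Several points on the other side are sound.

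- **Major violations.** This criterion could remove a patient with seven weeks off drug. A reader might infer that the patient certainly remains in the PP set; the documents support only that the patient can remain. The criterion is left open until just before database lock, however, in an open-label trial, so it does not replace a working rule.
- **The protocol.** A reader might infer that protocol 6.5 and 7.5.1 have the same defect. They name no visits, and step 4 shows that counting Week 9 removes the patient. What is established is the narrowing in SAP 2.2 and the possible mismatch between the documents.
- **Missing Visit 5.** It is tempting to say that a patient who never attends Visit 5 cannot fail twice. Compliance is computed from daily diary entries, and patients who stop drug are asked to continue them, so absence alone does not prevent a Week 12 value. A diary that stops does.
- **Materiality.** The study is descriptive, ITT is primary, and compliance and exposure are summarised and listed, so such a patient would be visible. Nor do the documents support an inference that the PP result would be inflated: if the drug works, keeping non-takers moves PP towards ITT.

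These points limit the size of the problem. They do not change the fact that the SAP's one explicit adherence criterion passes a patient with almost no maintenance dosing.

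**Conclusion.** The concern holds for SAP 2.2. As written, the compliance rule keeps a patient dosed to Day 35 and not after, with 12.5% of nominal maintenance days dosed (none under SAP 3.2), whichever of the look-backs examined is used. Results for earlier stops depend on the undefined look-back. Whether such a patient is finally in the PP set also depends on the undefined major-violation criterion, and the protocol can be read to give a different PP set.

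The documents state no discontinuation rate, so the number affected is unknown. Assuming 1 to 2 of about 30 patients, the share is 1/30 = 3.3% to 2/30 = 6.7%. The ITT primary analysis does not change. The correction is worth making because it is cheap and the PP repeat is the only sensitivity analysis.

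**What to change.** In SAP 2.2, and in matching words in protocol 6.5 and 7.5.1, replace the two-visit condition with one rule: exclude from PP any patient whose compliance with investigational product over the whole maintenance period is below 80%.

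- **Period:** maintenance as in SAP 3.2, from the day after Visit 4 through Visit 5, or through the scheduled end of Part A if Visit 5 is missed. Correct the Day 28 label on Visit 4 in SAP 3.2 at the same time.
- **Denominator, for this rule only:** all days in that period, with days after permanent discontinuation counted as not taken, in place of the reported-days denominator of SAP 3.1.3.7. Changing the threshold rule alone would not be enough, as step 6 shows.

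Under this rule every early stopper above scores 0/49, or 14/49 = 28.6% with a recorded taper, and is removed. A fully compliant patient scores 49/49 and stays.

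The cost is a short text change in both documents and no new data collection. The PP set may be slightly smaller. A patient who took drug but left diary gaps could also fall below 80%, so gaps should be queried against returned supplies, which SAP 4.1.6 already provides for, before database lock.
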